As this is a pilot evaluation of the acceptability and feasibility of providing CBT4CBT in a Black church setting, data analyses will focus on determining whether the results warrant further adaptation of the existing CBT4CBT program. Criteria for this will include (1) measuring acceptability of treatment by giving each participant a post-intervention satisfaction survey as well as a qualitative exit interview, to fully assesses satisfaction with the intervention, perception of outcome, attitudes about spiritual practices accompanying CBT modules, and whether the participant would recommend this program to a friend. (2) Feasibility will be measured by at least 2/3 of participants (N=27) completing the CBT4CBT intervention. Secondary analyses will include significant reductions in drug use, as measured by mean change scores in the severity and quantity of substance use, and functioning over the course of treatment intervention. The proposed sample size (n=40) is adequate to detect this effect.

SECTION VI: RESEARCH INVOLVING DRUGS, BIOLOGICS, PLACEBOS AND DEVICES

N/A

SECTION VII: HUMAN SUBJECTS

1. Subject Population: Provide a detailed description of the types of human subjects who will be recruited into this study.

Participants:

BSUD (20 male and 20 female) who self- identify as Black and want help with drug and/or alcohol problems in the church setting will be recruited from within the church itself, Dixwell Avenue Congregational UCC and the two predominately Black neighborhoods in New Haven, CT, Dixwell and Newhallville, immediately surrounding the church.

CHAs—12 Black church members and leaders who are well versed in the practices of the Black church will be recruited by [name] to serve in this role.

2. Subject classification: Check off all classifications of subjects that will be targeted for enrollment in the research project. Will subjects who may require additional safeguards or other considerations be enrolled in the study? If so, identify the population of subjects requiring special safeguards and provide a justification for their involvement.

- | | | |
|--|--|--|
|  Children |  Healthy |  Fetal material, placenta, or dead fetus |
|  Non-English Speaking |  Prisoners |  Economically disadvantaged persons |

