Because the projected effect sizes may not be large enough for detection during interim analyses, we are not proposing a preliminary analysis of accumulating efficacy and safety data by treatment. Instead, we propose to submit a quarterly report of aggregate data to the DSMB members that contains screening data, baseline demographics, retention data, serious adverse events data, as well as accrual status including projections, times to milestones, and any other data that will help in the assessment of the clinical trial. Based on this report, each DSMB member will complete a form making one of two recommendations: 1) continue recruitment as planned; or 2) schedule formal DSMB meeting immediately. If any DSMB member recommends a meeting, this will be scheduled within one week, minutes will be kept, the report will be reviewed with the PI, and the committee will vote on whether the study should: 1) continue recruitment unchanged; 2) continue with a protocol amendment; 3) stop recruiting pending further investigation. If, after this meeting, any DSMB member votes to stop recruitment or requests a protocol modification, the Yale IRB will be informed.

HIC# 2000022733

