Data Analysis Plan for a pilot feasibility study of providing substance use treatment in the Black Church

PI: [name] [name]
Data Manager: [name]

Updated 12/3/2020

This study is being conducted to determine the feasibility of recruiting Black adults with substance use disorder from within the Black Church and immediate surrounding community and retaining them in treatment, within a church setting.

A consort diagram will be used to assess the flow of participants from screening through week 8. Since this is a single arm trial cross tabs and ANOVA's will be run to describe the sample on characteristics such as age, sex, education, marital status.

1. We will measure acceptability of treatment by giving each participant a post-intervention satisfaction survey as well as a qualitative exit interview, to fully assesses satisfaction with the intervention, perception of outcome, attitudes about spiritual practices accompanying CBT modules, and whether the participant would recommend this program to a friend.

This will be done by calculating the mean and standard deviation of each question.

2. Feasibility will be measured by at least 2/3 of participants (N=27) completing the CBT4CBT intervention.

This will be a done by calculating the mean and standard deviation of number of sessions attended over the 8-week trial.

3. Secondary analyses will include significant reductions in drug use, as measured by mean change scores in the severity and quantity of substance use, and functioning over the course of treatment intervention.

As the study was implemented this outcome was refined to better reflect the aims of the study (recruiting and retention participants in treatment). A change score will not be calculated.

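### The protocol's claim that n=40 is adequate to detect change in substance use and functioning has no stated basis, and SAP item 3 drops the only analysis it could apply to

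*Protocol*

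**What the plan says.** Protocol Section V.5 (Statistical Considerations) sets two criteria for taking the programme further: acceptability, from a survey and exit interview, and feasibility, met if at least two thirds (27) complete the intervention. It then adds a secondary objective: "significant reductions in drug use, as measured by mean change scores in the severity and quantity of substance use, and functioning". The next sentence is the only sample-size justification in either document: "The proposed sample size (n=40) is adequate to detect this effect".

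The Data and Safety Monitoring Plan (Section IX.3) alludes to expected effects without giving a number: "Because the projected effect sizes may not be large enough for detection during interim analyses". That sentence explains why no interim analysis is proposed; it says nothing about the final sample.

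SAP item 3 repeats the secondary objective, says the outcome was refined while the study was under way so as to fit the recruitment and retention aims, and ends: "A change score will not be calculated". Acceptability and feasibility are summarized by means and standard deviations. Cross tabs and ANOVAs are listed only to describe the sample.

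Two protocol statements still depend on change in use. Aim 4 is to gather pilot data on the programme's effects on substance use, recovery goals and functioning. The Statement of Purpose makes early signs of reduced use, alongside acceptability and feasibility, a condition for adapting the programme and running a randomized trial.

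**The concern.** A statement that a sample is adequate to detect an effect has meaning only relative to a magnitude, a variability, a significance level and a power. Section V.5 names the outcomes and the direction but supplies none of these, and it makes one claim for at least three quantities (severity of use, quantity of use, functioning) that need not share a standardized effect. Once the SAP removes the change score, the claim no longer refers to any planned analysis.

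What is at stake is the decision the pilot feeds. A reader of the protocol would believe the study was sized to judge whether use falls. A reader of the SAP would find no planned summary of that change at all. Any statement about reduced use in support of the next trial would then rest either on nothing or on an analysis not specified in the plan.

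**Working it through.** **Inputs from the documents.** n = 40, single arm; five cohorts of 8 (Section B.2); 8 weeks of treatment; feasibility threshold 27 of 40 (Section V.5, Figure 2). Effect size, SD of change, alpha, sidedness, power, dropout allowance and intracluster correlation are not stated. The claim therefore cannot be reproduced, and the check asks instead what 40 could detect.

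**Assumptions.** Paired (one-sample) t-test on the change; d = mean change / SD of change; two-sided alpha 0.05; 80% power, with variants below.

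**Detectable change.** The normal approximation is d = (1.960 + 0.842)/√n.
- n = 40: 2.802/6.325 = 0.443
- n = 27: 2.802/5.196 = 0.539

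The exact values solve, for d, power = 1 − F(t*; n−1, d√n) + F(−t*; n−1, d√n), where F is the noncentral t distribution function and t* is the 97.5% point of t on n−1 df:

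| Test and power | 40 pairs | 27 pairs |
|---|---|---|
| Two-sided 5%, 80% | 0.454 | 0.560 |
| Two-sided 5%, 90% | 0.526 | 0.648 |
| One-sided 5%, 80% | 0.400 | 0.491 |
| One-sided 5%, 90% | 0.471 | 0.579 |

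**Power for given changes (two-sided 5%).**

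| d | 40 pairs | 27 pairs |
|---|---|---|
| 0.3 | 46% | 32% |
| 0.4 | 69% | 52% |
| 0.5 | 87% | 71% |
| 0.6 | 96% | 85% |

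Pairs needed for 80% power: 90 at d = 0.3, 52 at 0.4, 34 at 0.5, 24 at 0.6. So 40 is adequate for some plausible values and not for others, and the protocol does not say which it had in mind.

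**Clustering, as a sensitivity case.** Effective n = 40/(1 + 7 × ICC). For assumed ICCs of 0.01, 0.05 and 0.10 this is 40/1.07 = 37.4, 40/1.35 = 29.6 and 40/1.70 = 23.5. The detectable d at 80% power (normal approximation) is 0.46, 0.52 and 0.58. The documents give no basis for choosing among these.

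**What 40 gives for feasibility.** 2/3 × 40 = 26.7, rounded up to 27, which agrees with the protocol; 27/40 = 67.5%, leaving 13 non-completers. The exact (Clopper-Pearson) 95% interval for 27/40 is 50.9% to 81.4%.

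**What 40 gives for estimating change.** The half-width of a 95% interval, in SDs of the change, is t*/√n: 2.023/6.325 = 0.32 with 40 pairs and 2.056/5.196 = 0.40 with 27.

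**The case against.** The strongest reply is that nothing here proves the sentence wrong. That stands. A reader might infer from the missing inputs that 40 is too small. The documents do not support this: if the investigators had d = 0.5 in mind, 40 pairs give 87% power. Nor does a later SAP that drops the analysis make the earlier sentence false; it leaves it without an object.

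A reader might also take 27 as the planned analysis set, or as a planned one-third loss. It is neither. It is a success threshold that tolerates 13 non-completers, although Figure 2 labels it retention. Finishing the modules is not the same as supplying outcome data: the protocol plans to re-interview everyone after treatment, and Table 2 schedules the substance-use calendar, urine and breath tests and the symptom inventory weekly. With no dropout allowance stated, 27 is a fair sensitivity case and no more.

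It would likewise go too far to say that no effect is named, or that the SAP contains no tests. Outcome and direction are given, and ANOVAs are listed to describe the sample.

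Finally, the outcome is secondary in a single-arm pilot, Section V.5 numbers only acceptability and feasibility as criteria, and early promise does not require a significance test. This limits the importance of the point and argues against restoring a test. It does not remove the need for some planned summary of change, because the Statement of Purpose and Aim 4 both rely on one.

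**Conclusion.** The adequacy claim is unsupported and, under the current SAP, applies to no analysis, while two protocol statements still need information on change in use. It is not shown that 40 is too few. Whether 40 suffices depends on an unstated standardized change: about 0.45 or more with 40 complete pairs, or about 0.56 or more with 27. These figures assume a paired t-test, two-sided 5%, 80% power and independent participants; clustering by cohort would raise them by an amount the documents do not allow one to fix. The point is worth correcting because the repair changes what the pilot can report towards the next trial, but it concerns a secondary outcome and does not touch the feasibility or acceptability criteria.

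**What to change.** 1. In Section V.5, delete the adequacy sentence.
2. In its place, state what 40 provides: if 27 of 40 complete, the exact 95% interval for completion is 51% to 81%; and, for a paired t-test at two-sided 5%, 80% power corresponds to a standardized change of 0.45 with 40 pairs and 0.56 with 27. Label 27 as the feasibility threshold, not an expected loss. Do not add a reason why 40 was chosen unless the investigators can supply one; the documents give none.
3. In SAP item 3, replace the sentence that drops the change score with descriptive pre-post change in substance use and functioning, reported as estimates with 95% intervals and without a claim of significance. Name one instrument and time window for each. For functioning the choice must be explicit, because Figure 2 names a social functioning scale that the Table 2 battery does not list.
4. Bring the wording on significant reductions in Section V.5 into line with item 3.

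The cost is a few sentences in each document, a sample-size justification that reads less favourably, and a small amount of analysis of data the protocol already schedules. No extra participants are needed.

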Data Analysis Plan for a pilot feasibility study of providing substance use treatment in the Black Church

PI: [name] [name]
Data Manager: [name]

Updated 12/3/2020

This study is being conducted to determine the feasibility of recruiting Black adults with substance use disorder from within the Black Church and immediate surrounding community and retaining them in treatment, within a church setting.

A consort diagram will be used to assess the flow of participants from screening through week 8. Since this is a single arm trial cross tabs and ANOVA's will be run to describe the sample on characteristics such as age, sex, education, marital status.

1. We will measure acceptability of treatment by giving each participant a post-intervention satisfaction survey as well as a qualitative exit interview, to fully assesses satisfaction with the intervention, perception of outcome, attitudes about spiritual practices accompanying CBT modules, and whether the participant would recommend this program to a friend.

This will be done by calculating the mean and standard deviation of each question.

2. Feasibility will be measured by at least 2/3 of participants (N=27) completing the CBT4CBT intervention.

This will be a done by calculating the mean and standard deviation of number of sessions attended over the 8-week trial.

3. Secondary analyses will include significant reductions in drug use, as measured by mean change scores in the severity and quantity of substance use, and functioning over the course of treatment intervention.

As the study was implemented this outcome was refined to better reflect the aims of the study (recruiting and retention participants in treatment). A change score will not be calculated.

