NOTE: The requirement for maintaining a current disclosure form on file with the University's Conflict of Interest Office extends primarily to Yale University and Yale-New Haven Hospital personnel. **Whether or not they are required to maintain a disclosure form with the University's Conflict of Interest Office, all investigators and individuals deemed otherwise responsible by the PI who are listed on the protocol are required to disclose to the PI any interests that are specific to this protocol.**

SECTION II: GENERAL INFORMATION

1. **Probable Duration of Project:** State the expected duration of the project, including all follow-up and data analysis activities.

The duration of the pilot in its entirety will be 1 year; March 2018-March 2019

2. **Targeted Enrollment:** Give the number of subjects: 40

a. targeted for enrollment at Yale for this protocol 40 If this is a multi-site study, give the total number of subjects targeted across all sites N/A

b expected to sign the consent form 60

c. expected to complete some or all interventions for this protocol? 40

SECTION III: FUNDING, RESEARCH TEAM AND TRAINING

1. **Funding Source:** In IRES
2. **Research Team:** In IRES

SECTION V: RESEARCH PLAN

1. **Statement of Purpose:** State the scientific aim(s) of the study, or the hypotheses to be tested.

HIC# 2000022733

We will conduct a pilot study evaluating the feasibility and acceptability of providing a computer-based program (CBT4CBT), used for the treatment of substance use disorders, in a church setting. Forty Black adults with a current DSM-5 alcohol or substance use disorder will utilize the ‘CBT for CBT’ program over a period of 8 weeks. Primary outcomes will be acceptability and feasibility of providing the treatment in a church setting. If found to be acceptable and feasible, with preliminary promise for reductions in substance use, the next step would be to adapt the computer intervention for this population and conduct a randomized controlled trial.

Specific aims are as follows:

- (1) To determine the feasibility of recruiting Black adults with substance use disorders (BSUD) from within the Black church and immediate surrounding community and retaining BSUD in treatment, within a church setting.
- (2) To evaluate the acceptability of CBT4CBT with BSUD in a church setting and to identify if religious behaviors led by trained church based health advisors (CHA), may increase the likely suitability of this intervention within the Black church.

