- (3) To obtain qualitative data from both CHAs and BSUD about providing substance abuse treatment in a church setting.
- (4) To collect pilot data about the effects of CBT4CBT on substance use, recovery goals and level of functioning among BSUD.

2. **Background:** Describe the background information that led to the plan for this project. Provide references to support the expectation of obtaining useful scientific data.

A. SIGNIFICANCE

A.1. Overview of Research Activities

The overall aim of this proposal is to provide Black adults with substance use disorders (BSUD) access to an evidence-based, web-based, cognitive behavioral therapy intervention (CBT4CBT) and to pilot test it in a church setting. Given low rates of substance abuse treatment initiation and engagement as well as the importance of spirituality and the Black church amongst Black adults, this study will assess the feasibility and acceptability of conducting CBT4CBT in a Black church setting, and measure the effect of CBT4CBT on participant’s substance use, recovery goals and level of functioning.

A.2. BSUD suffer more negative drug-related consequences, but less likely to initiate treatment

Substance Use Disorders (SUD) are one of the most devastating health and social issues confronting this country, causing a tremendous amount of suffering for individuals, families, entire communities, and disproportionately affect minority communities. Black adults use alcohol at lower rates compared with their white counterparts (43.6% vs 57.7%), with nicotine and illicit drug use at the same rate, however Blacks are more likely to suffer negative drug-related consequences, including physical ailments and higher rates of involvement in the criminal justice system. Despite this disparity, Blacks are less likely to initiate substance use treatment when compared with other racial groups, but the reasons accounting for this difference are not well understood. Several theories have been cited for low treatment engagement among Blacks, including societal and cultural stigma associated with accessing substance use treatment,

HIC# 2000022733

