- Clinical deterioration. We will closely monitor participant treatment response and safety in all conditions through assessment sessions. These will include breath and urine screens with assessment of psychiatric status. Although in our experience this is a very rare event in behavioral trials, participants who show significant deterioration (e.g., increased substance use or psychiatric symptoms that cannot be managed within the protocol) will be regarded as symptomatic failures, withdrawn from the study, and referred appropriately.
- Strategies to minimize attrition. In order to hold participant dropout to a minimum, we use multiple procedures to enhance adherence with alcohol and substance abuse treatment. These include rapid assignment treatment days, thorough explanation of study treatments and requirements, close monitoring of participants' clinical status, integration of the research with community and church, accessibility of study staff for questions and problems, and adequate compensation to participants for the time spent on completing assessment instruments.

(3) Post treatment assessment

At the end of the 8-week treatment period, all participants (BSUD) will be re-interviewed by the research assistant, who will complete post-treatment ratings (see Assessments, below) and by the PI, who will complete qualitative exit interviews with both the BSUD and CHAs about their experience in the research project. Access to the CBT4CBT program will be terminated for participants after the exit interviews. Participants will be strongly encouraged to continue substance abuse treatment at the end of the study, and resources/information about local substance abuse and mental health clinics will be made available.

(4) Study Termination

Participants will be withdrawn from the study if they show severe psychological or symptomatic deterioration, unacceptable levels of adverse events as determined by the PI [name] or other research staff. Participants withdrawn from the study will be offered treatment as usual at a local clinic or be referred to a higher level of care when appropriate. Private referral and/or hospitalization may also be offered according to the participants' needs and wishes.

[figure not shown]
(5) Assessments

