Assessments include measures used to: 1) Describe the sample, 2) Measure primary and secondary outcomes during treatment. We will rely on widely used, well-validated instruments. Please see a complete list of the Assessment Battery Below in **Table 2**.

Table 2 Assessment Battery

Instrument name	Interview or self-report	Rater	Screen	Pre Tx	Weekly	Monthly	Post Tx (8 wks)
Informed Consent Quiz	Self-report	P	X				
*Baseline Demographics	Interview	RA	X				
Inclusion/Exclusion criteria	Interview	RA	X				
Follow-up contact & tracking sheet		RA	X				X
DSM-5 Criterion Checklist	Interview	RA	X				X
Urine toxicology screen, breathalyzer		RA	X	X	X		X
Timeline Follow-back/ Substance Use Calendar (SUC)	Interview	RA	X		X		X
Brief Symptom Inventory (BSI)	Interview	RA		X	X		X
Quality of Life Scale	Interview	RA		X			X
Treatment Utilization	Interview	RA		X		X	X
Evaluation of treatment, endpoint	Self-report	P					X
Daily Spiritual Scale	Self-report	P		X			X
Multi Group Ethnic Identity Measure	Self-report	P		X			X
Racial Pride Scale	Self-report	P		X			X
Recovery Markers Questionnaire	Self-report	P		X			X
Religiosity Scale	Self-report	P		X			X
Religious Methods of Coping to Gain Control	Self-report	P		X			X
Sense of Community Index	Self-report	P		X			X
*Qualitative Exit Interview Guide	Interview	PI					X

*CHAs will complete Baseline Demographics and Qualitative Exit Interviews only

A pictorial overview of the pilot study is outlined below in **Figure 2**.

Figure 2: Overview of Pilot Study: 40 participants, divided into 5 cohorts of N=8, (1) Feasibility (2/3 Retention

HIC# 2000022733

N=27); (2) Acceptability (Evaluation of Treatment Survey, Qualitative Exit Interview); (3) Substance Use (Urine Tox, Breathalyzer); (4) Recovery Goals (Recovery Markers Questionnaire); (5) Functioning (Social Functioning Scale)

4. Genetic Testing N/A

5. Statistical Considerations: Describe the statistical analyses that support the study design.

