BSUD subjects will be compensated for time required to complete screening assessments at \$20, baseline assessment at \$20, week 4 assessments at \$10, study assessments at \$10 for each weekly module time point; \$50 for completing all modules, and \$50 at post-treatment for a possible total of \$230.

CHA subjects will be paid \$14.25 per hour by check for the time participated in the project, including time spent in the confidentiality and addiction trainings led by [name], as well as the qualitative interviews. The research team anticipates approximately 86 hours of time in the project, over an 8-12 week time period, for a total of \$1,225.50 paid by check.

3. **Costs for Participation (Economic Considerations):** Clearly describe the subject's costs associated with participation in the research, and the interventions or procedures of the study that will be provided at no cost to subjects.

There will be no costs to subjects associated with participation in this study. Subjects will not be charged for study treatments or evaluations they receive at the clinic.

4. **In Case of Injury:** This section is required for any research involving more than minimal risk.
 - a. Will medical treatment be available if research-related injury occurs?
 - b. Where and from whom may treatment be obtained?
 - c. Are there any limits to the treatment being provided?
 - d. Who will pay for this treatment?
 - e. How will the medical treatment be accessed by subjects?

Because we are evaluating standard behavioral approaches with strong empirical support and no known adverse consequences, study related injuries are expected to be extremely rare. There will be no compensation and/or medical treatment available if injury occurs. Participants or their insurance carrier will be expected to cover costs of any medical treatment.

LITERATURE CITED

REFERENCES

1. Satcher D. Mental Health: Culture, Race, and Ethnicity—A Supplement to Mental Health: A Report of the Surgeon General. 2001. <http://www.ncbi.nlm.nih.gov/books/NBK44243>. Accessed June 25, 2016.
2. National Institute on Drug Abuse. Drug Use Among Racial/Ethnic Minorities. NIH Publication No. 03-3888, Printed 1995, Revised September 1998. Revised 2003.
3. Galvan FH and Caetano R. Alcohol use and Related problems among ethnic minorities in the United States. *Alcohol Res Health*. 2003;27(1):87-94.

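### Does acceptability need a pass mark and a rule for missing week-8 surveys before its results can be used?

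*SAP*

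**What the plan says.** The protocol's Statement of Purpose (Section V.1) makes acceptability and feasibility the primary outcomes and ties the next step to both: "If found to be acceptable and feasible, with preliminary promise for reductions in substance use", the intervention would be adapted and taken to a randomised trial. Statistical Considerations (Section V.5) lists what will inform that decision. For acceptability the text is "Criteria for this will include (1) measuring acceptability of treatment by giving each participant a post-intervention satisfaction survey" together with an exit interview; for feasibility it is completion by at least two-thirds, N=27.

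The SAP repeats both items. Under acceptability it adds only "This will be done by calculating the mean and standard deviation of each question".

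On timing, Table 2 schedules the survey ("Evaluation of treatment, endpoint") and the exit interview at the post-treatment visit alone. The post-treatment assessment text in Section V.3 says that "all participants (BSUD) will be re-interviewed by the research assistant", with the investigator doing the exit interviews. The clinical deterioration paragraph says that participants who worsen markedly "will be regarded as symptomatic failures, withdrawn from the study, and referred appropriately"; it describes no exit survey for them and expects such cases to be very rare. Specific Aim 3 is "To obtain qualitative data from both CHAs and BSUD about providing substance abuse treatment in a church setting", and neither document names a method for analysing those interviews.

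**The concern.** Set beside feasibility, the acceptability item looks unfinished. One primary outcome has a number that can be missed; the other is met, on a literal reading, once the survey has been handed out. If the two outcomes together decide on a randomised trial, a reader wants to know in advance what result would count against going on.

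The second worry is who answers. A survey given only at week 8 may miss people who left early, and they may be the least satisfied. The respondent mean would then be too favourable by the missing fraction times the gap in scores. The CONSORT diagram and the count of completers show that people left, not what they thought. The third worry is that a mean and SD cannot summarise interview text, so half of the acceptability evidence has no stated analysis.

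At stake would be a decision to proceed that rests on an over-favourable picture of how the programme was received.

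**Working it through.** **The plan's own figure.** Two-thirds of 40 is 40 × 2/3 = 26.67, rounded up to 27, which agrees with both documents. Feasibility can therefore be met with up to 40 − 27 = 13 non-completers. Acceptability has no figure to reproduce.

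**Inputs.** N = 40 is from the protocol. The documents give no survey non-response, no share who would recommend the program, no response scale and no score gap. The values below are assumptions: 0, 4, 8 or 13 surveys missing, about 88–90% of respondents favourable, and a gap of 1 point on an item. The 13 is the largest non-completion that the feasibility mark allows. It treats every non-completer as a non-respondent, which the protocol does not say.

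**Bounds over all enrolled.** With f favourable among m respondents, the share of all 40 lies between f/40 and (f + 40 − m)/40. The shift in an item mean is (missing/40) × gap.

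| Missing | Favourable / respondents | Exact 95% CI | Range over all 40 | Shift for a 1-point gap |
|---|---|---|---|---|
| 0 | 36/40 = 90.0% | 76.3–97.2% | 90.0% | 0 |
| 4 | 32/36 = 88.9% | 73.9–96.9% | 80.0–90.0% | 4/40 = 0.10 |
| 8 | 28/32 = 87.5% | 71.0–96.5% | 70.0–90.0% | 8/40 = 0.20 |
| 13 | 24/27 = 88.9% | 70.8–97.6% | 60.0–92.5% | 13/40 = 0.325 |

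**Would the reading change?** Take 27 of 40 as an illustrative mark. With 4 missing, 32 favourable already exceeds 27; with 8 missing, 28 does. In both cases the views of those missing cannot overturn it. With 13 missing, 27 − 24 = 3 of the 13 would have to be favourable.

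**Would a pass mark help?** Apply two-thirds to respondents. With 27 respondents the mark is 27 × 2/3 = 18. At 18/27 = 66.7% the exact 95% CI is 46.0–83.5%. If the true rate is 60%, the chance of at least 18 of 27 (binomial) is 0.31. Such a rule would pass nearly a third of the time at a true rate below its own mark, and its denominator would shrink as surveys go missing, which is the very complaint. The two-thirds figure is also a retention target; nothing in the documents supports it as a satisfaction target.

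**What already guards the result.**
- Both documents direct the survey at each participant, and the re-interview is planned for all participants, not for completers.
- Section XI.2 pays $50 for completing all modules and a separate $50 "at post-treatment for a possible total of" $230, so someone who skipped modules still has a reason to attend.
- Table 2 has a contact and tracking sheet at screening and post-treatment.
- The quarterly DSMB report (Section IX.3) covers completeness of primary outcome data.
- The SAP's CONSORT diagram runs to week 8, so the denominator will be visible.

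**The case for a change.** The strongest case for a change is that the documents themselves give acceptability a deciding role. This is not a descriptive extra, and the authors showed with feasibility that a small pilot can carry a simple benchmark. An intention to reach everyone is not an analysis rule. Counting losses does not say how a person without a survey enters the result. Naming a key item, a denominator and an interview method would cost a few lines of SAP text.

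Much of the factual part stands: there is no pre-specified cut-off, no written denominator and no named qualitative method. It does not stand that no result could count as unacceptable. Low item means, few participants recommending the program or critical interviews would all be plain to a reader; what is missing is a number fixed beforehand. The bias argument stands only conditionally, because both of its ingredients are assumed.

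The possible remedies add little. Stating the number surveyed, giving an interval for a proportion and analysing interviews by theme are what a competent analyst would do when writing this up. A survey at the point of leaving would need a protocol amendment and extra contacts, and would mix ratings made after different lengths of exposure. The SAP is dated 12/3/2020 and the project was planned for March 2018 to March 2019, so that survey is probably no longer possible, and a new cut-off would probably be set after data had been seen.

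**Conclusion.** No change follows. The gap is real but of the kind that analysts fill sensibly. The planned item means and SDs describe acceptability soundly for a single-arm pilot of 40, and the survey is aimed at everyone enrolled.

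On the assumed 88–90% favourable, the illustrative two-thirds reading is unaffected by 4 or 8 missing surveys; with 13 missing it is lost only if fewer than 3 of those 13 would recommend the program. A 1-point gap would move an item mean by at most 0.325 in that extreme case, and by nothing if those missing are equally satisfied. These sizes depend on the assumed response pattern: a favourable share nearer two-thirds would leave less margin.

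Descriptive reporting of several items alongside interviews is a fair choice here. A cut-off borrowed from retention and added in late 2020 would give the appearance of a test without its protection.
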